6.5.3. Extrapyramidal Symptom Rating Scale-Abbreviated (ESRS-A)

The ESRS-A is an abbreviated manualized version of the ESRS, a semi-structured interview that rates parkinsonian symptoms, dystonia, dyskinesias, and akathisia over the previous 7 days. The ratings include a motor examination for rigidity, tremor, reduced facial expression or speech, impaired gait/posture, postural instability, and bradykinesia/hypokinesia. Twenty-four individual items are rated on a 6-point scale: 0=Absent, 1=Minimal, 2=Mild, 3=Moderate, 4=Severe, or 5=Extreme. Frequency is included as an index of severity. Symptoms are divided into the 4 corresponding subscales and each subscale is summarized in a Clinical Global Impression of Movement Severity (CGI-MS) score.

For each of the 24 individual items, as well as for the 4 subscales, a frequency distribution will be provided by treatment group at each time point.

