#### 1.4. Overall Risk and Benefit Assessment

As further described in Section 1 and the rationale for this study (Section 1.3), MDD is a common, serious, recurrent mental disorder. MDD is the leading cause of disability, and its prevalence is rising.

Current therapies commonly used as first-line ADT in patients with MDD (eg, SSRIs and SNRIs) are sub-optimally effective in some patients who require adjunctive treatment, or who are otherwise poorly compliant because of their associated AEs, such as weight gain and sexual side effects. Currently approved adjunctive treatments are limited to the atypical antipsychotic drug class, which present considerable tolerability concerns (eg, metabolic syndrome, akathisia, and EPS). The orexin-receptor antagonist class offers a novel mechanism of action that may prove to be a valuable alternative in the adjunctive treatment of MDD, but without the side effects observed with other medications commonly used in this setting, such as weight gain, sexual side effects, akathisia, or EPS. CCI

The currently available data (see Section 1.1.2, Clinical Studies, and the JNJ-42847922 Investigator's Brochure) support this clinical study that investigates the efficacy and safety of JNJ-42847922 in adult subjects with MDD who have responded inadequately to commonly used first-line ADTs.

The antidepressant effect of JNJ-42847922 was clinically relevant as early as Day 11 of exposure and was sustained at least 14 days after treatment discontinuation. The effect of JNJ-42847922 was largely related to an effect on the core symptoms of depression, and overall unrelated to its effect on sleep-related events.

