
 
To assess the effect of JNJ-42847922 compared to quetiapine XR as adjunctive therapy for MDD on hormonal stress-response via HPA axis function.
 
	
 
Change from baseline to Weeks 6 and 24 in salivary cortisol levels as measured at home upon awakening and at home
 

Objectives	Endpoints

 
To assess the safety and tolerability of JNJ-42847922 compared with quetiapine XR as adjunctive treatment in subjects with MDD.
 
	
during the evening.
 
 
Safety assessments including: 
 
Adverse events (AEs).
 
Proportion of all SAEs and events of special interest (eg, parasomnias).
 
Vital signs, physical examinations, ECG, and laboratory parameters.
 
Sexual functioning using the Arizona Sexual Experiences Scale (ASEX).
 
Extrapyramidal symptoms assessed by the Extrapyramidal Symptom Rating Scale-Abbreviated (ESRS-A).
 
Suicidality assessed using the C-SSRS.
 
Potential withdrawal effects assessed by the Physician Withdrawal Checklist (PWC).
 
 
 

Exploratory	

 
To collect medical resource utilization (MRU) data that may be used in future economic modeling.
 
	
 
Healthcare Resource Use Questionnaire (HRUQ).
 

 
To assess the effect of JNJ-42847922 compared with quetiapine XR as adjunctive therapy for MDD on self-reported measures of sleep.
 
	
 
Change from baseline in subjective sleep parameters as measured by the Consensus Sleep Diary-Morning Administration (CSD-M) after the first 6 weeks of treatment (using the average of 3 morning measurements in Week 6).
 
Change from baseline in subjective sleep parameters as measured by the CSD-M after 3 to 6 months of treatment (using the average of 3 morning measurements in Weeks 12, 18, and 24, respectively).
 

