### **Safety Evaluations**

Standard safety evaluations including collection of AEs and concomitant medications, physical examination, body weight, waist circumference, vital signs, 12-lead ECG, urine drug test, alcohol breath test, pregnancy testing, and clinical laboratory tests will be performed to monitor subject safety throughout the study.

The homeostatic model assessment will be conducted to estimate changes in beta-cell function and insulin sensitivity. The model requires both glucose and insulin measurements. It is known that atypical antipsychotic medications, including quetiapine XR, may cause insulin resistance; at present, there is no evidence that JNJ-42847922 has any impact on glucose metabolism.

Emergence of suicidal ideation will be assessed using the C-SSRS. The C-SSRS has been used frequently in clinical studies and it is a standard measure for suicidal ideation assessment; its use is in accordance with Food and Drug Administration (FDA) guidance.

The effect on sexual functioning will be measured by the ASEX. The ASEX has shown satisfactory reliability and validity.

Drug-induced EPS will be monitored using the ESRS-A. The ESRS-A is an abbreviated manualized version of the ESRS, a semi-structured interview that rates parkinsonian symptoms, dystonia, dyskinesias, and akathisia over the previous 7 days. The ESRS-A is being included since the comparator medication, quetiapine XR, is an antipsychotic with the potential to cause EPS and akathisia.

In addition, potential withdrawal effects will be assessed by the clinician using the PWC. The PWC is a reliable and sensitive instrument for the assessment of discontinuation symptoms.

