### **11.2. Sample Size Determination**

The primary purpose of the study is to investigate potential differentiating features between JNJ-42847922 and quetiapine XR. Although the sample size was not chosen based on a specific set of endpoints, for evaluating the time to discontinuation of study drug in the JNJ-42847922 group versus the quetiapine XR group, a one-sided log-rank test with an overall sample size of 100 subjects (50 in the JNJ-42847922 group and 50 in the quetiapine XR group) provides approximately 92% power at a 1-sided 0.10 significance level to detect a hazard ratio of 0.415, assuming the proportion of subjects who discontinue from study drug in the quetiapine XR group is 50%. The planned sample size of the study is consistent with the nature of a Phase 2 exploratory study.

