		4	Week 2	2 to 28	14
		6	Week 6	29 to 63	42
		7	Week 12	64 to 105	84
		8	Week 18	106 to 147	126
	9	Week 24	148 to end of DB	168	
DB last visit	End point (DB)	2 to end of DB			
CSD-M	DB	Prior to Visit 2	Average Predose	≤1	-2, -1, 1
		Prior to Visit 6	Week 6 (Average)	2 to 63	40, 41, 42

Parameter	Analysis Phase	Scheduled Visit Number	Time Interval (label on output)	Time Interval (Day)*	Target Time Point (Day/Time)
		Prior to Visit 7	Week 12 (Average)	64 to 105	82, 83, 84
		Prior to Visit 8	Week 18 (Average)	106 to 147	124, 125, 126
		Prior to Visit 9	Week 24 (Average)	148 to end of DB	166, 167, 168
		DB last visit	End point (DB)	2 to end of DB	
HRUQ	DB	2	Baseline	≤1	1
		6	Week 6	2 to 63	42
		7	Week 12	64 to 105	84
		8	Week 18	106 to 147	126
		9	Week 24	148 to end of DB	168
	DB last visit	End point (DB)	2 to end of DB		
	Follow-up	10	Follow-up	End of DB + 1 to end of FU	182
Physical Exam	Screening	1	Screening	<1	-28 to -1
	DB	1	Baseline	≤1	-28 to -1
		9	Week 24	2 to end of DB	168
		DB last visit	End point (DB)	2 to end of DB	
ISI	Screening	1	Screening	<1	-28 to -1
	DB	2	Baseline	≤1	1
Serum Chemistry, Urinalysis, Hematology, Lipid Panel, Weight, BMI, Waist Circumference	Screening	1	Screening	<1	-28 to -1
	DB	2	Baseline	≤1	1
		6	Week 6	2 to 63	42
		7	Week 12	64 to 126	84
		9	Week 24	127 to end of DB	168
		DB last visit	End point (DB)	2 to end of DB	
HbA1c, TSH, FT ₄	Screening	1	Screening	<1	-28 to -1
	DB	1	Baseline	≤1	-28 to -1
		7	Week 12	2 to 126	84
		9	Week 24	127 to end of DB	168
		DB last visit	End point (DB)	2 to end of DB	
ECG	DB	1	Screening	<1	-28 to -1
		1, 2	Predose	≤1	-28 to 1
		1, 2	Average Predose	≤1	1
		6	Week 6	2 to 105	42
		9	Week 24	106 to end of DB	168
		DB last visit	End point (DB)	2 to end of DB	
ASEX	DB	2	Baseline	≤1	1
		7	Week 12	2 to 126	84
		9	Week 24	127 to end of DB	168
		DB last visit	End point (DB)	2 to end of DB	
ESRS-A	DB	4	Week 2	2 to 21	14
		5	Week 4	22 to 35	28
		6	Week 6	36 to 63	42
		7	Week 12	64 to 126	84
		9	Week 24	127 to end of DB	168
		DB last visit	End point (DB)	2 to end of DB	
PWC ^a	DB	10	End point (DB)	2 to end of DB	

Parameter	Analysis Phase	Scheduled Visit Number	Time Interval (label on output)	Time Interval (Day)*	Target Time Point (Day/Time)
	Follow-up	10	Follow-up	End of DB + 1 to end of FU	182

*Relative to Study Day 1; DB=double-blind; FU=follow-up

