2.8. Baseline and End point (DB)

Baseline is defined as the last observation prior to the start of the first study agent administration, with the exception of the average predose ECG measurement and the average predose CSD-M measurement, which is defined as the average of all predose ECG results collected up to and

including the day of the first dose of study agent and the average of all predose CSD-M measurements collected up to and including the day of the first dose of study agent, respectively.

End point (DB) is defined as the last available postbaseline result within the double-blind phase. Unscheduled visit results are included in this definition and will be considered as the end point value if the unscheduled visit result is the last postbaseline result available within the double-blind phase.

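### The ESRS-A has no pre-dose rating, so it shows extrapyramidal symptoms present after dosing in each arm but not which are new or worse; one Day 1 rating would close the gap

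*SAP*

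**What the plan says.** The protocol's Study Design Rationale (3.2, Safety Evaluations) states the purpose of the scale: "Drug-induced EPS will be monitored using the ESRS-A". It gives the reason as follows: "The ESRS-A is being included since the comparator medication, quetiapine XR, is an antipsychotic with the potential to cause EPS and akathisia". Protocol 2.1 lists ESRS-A-assessed extrapyramidal symptoms among the safety assessments under the secondary safety and tolerability objective.

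The Time and Events Schedule marks the ESRS-A at Visits 4, 5, 6, 7 and 9, and at Visit 10 for early withdrawals only. Visit 1 (screening), Visit 2 (Day 1) and Visit 3 (telephone) are blank. The first ESRS-A row of SAP Table 1 reads "ESRS-A DB 4 Week 2 2 to 21 14", and no baseline row precedes it. The protocol also asks for the scale when the dose is changed, which is necessarily after dosing has begun.

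On analysis, SAP 6.5.3 says that for the 24 items and the 4 subscales "a frequency distribution will be provided by treatment group at each time point". Protocol 11.8 says only that results are tabulated by treatment. SAP 2.8 sets the general rule: "Baseline is defined as the last observation prior to the start of the first study agent administration".

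**The concern.** A scale meant to detect symptoms caused by a drug needs to know what was there before the drug. Without that, a subject rated with mild tremor or akathisia at Week 2 may have developed it on treatment or brought it into the study.

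Pre-existing findings are plausible in this population. Every subject takes an SSRI or SNRI. Antipsychotics are barred only from 4 weeks before Day 1 (Protocol 8), and SAP 2.6 defines a subgroup by earlier adjunctive antipsychotic use. The exclusion criteria name a history of neuroleptic malignant syndrome or tardive dyskinesia, but not other EPS, akathisia or tremor.

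What is at stake is how each arm's EPS results can be read. Protocol 11.2 opens with "The primary purpose of the study is to investigate potential differentiating features between JNJ-42847922 and quetiapine XR", and Protocol 1.4 names effects that the new class might avoid: "such as weight gain, sexual side effects, akathisia, or EPS". Any statement about how often EPS emerged on either drug would have no rated starting point.

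**Working it through.** The plan states no ESRS-A figure to reproduce, so the check is mainly a comparison of texts, followed by one illustration.

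**1. Is the baseline really absent?** The schedule's ESRS-A row has its first mark at Visit 4 (Day 14). SAP Table 1 separately starts the scale at Week 2 (Days 2 to 21). Two documents agree, so this is not a broken table. The same schedule does mark the ASEX and the C-SSRS at Visit 2.

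**2. Could a baseline come from elsewhere?** Under SAP 2.8 it must precede the first dose. The only unscheduled ESRS-A trigger is a dose change. The scale looks back 7 days, so a rating at Day 14 (window ±3 days) covers only days on drug. No baseline can be derived.

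**3. What follows for the analysis?** The planned frequencies are post-baseline prevalence. Change, shift and treatment-emergent worsening are undefined for this scale.

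**4. How much could the mixture matter within one arm?** Assumptions, since the documents give no EPS rates:
- a proportion p has a pre-existing symptom that persists, with p = 5%, 10% or 20%;
- a proportion e = 10% of the remaining subjects develop a new one.

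Observed prevalence = p + (1 − p)e. Share that predates dosing = p / [p + (1 − p)e].

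| p | Observed prevalence | Share predating dosing |
|---|---|---|
| 5% | 0.05 + 0.95 × 0.10 = 14.5% | 0.05 / 0.145 = 34% |
| 10% | 0.10 + 0.90 × 0.10 = 19% | 0.10 / 0.19 = 53% |
| 20% | 0.20 + 0.80 × 0.10 = 28% | 0.20 / 0.28 = 71% |

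The planned tables cannot show this split.

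**5. Does the mixture bias the comparison of arms?** Let the new-onset proportions be e1 and e2, with the same p expected in both arms by randomisation. The difference is [p + (1 − p)e1] − [p + (1 − p)e2] = (1 − p)(e1 − e2). The pre-existing term cancels. With e1 = 10%, e2 = 1% and p = 10%, the difference is 0.90 × 0.09 = 8.1 percentage points, which is the difference between arms in the proportion of all subjects with a new symptom. The arm difference is therefore not biased in expectation; what is missing is each arm's own new-onset rate.

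**6. One qualification.** The cancellation applies to subjects as randomised. The sample-size assumptions (50 per arm, 50% discontinuing on quetiapine XR, hazard ratio 0.415) imply 1 − 0.5^0.415 = 25% discontinuing on JNJ-42847922 under proportional hazards. That leaves about 25 and 37 subjects still on treatment at Week 24. Without a baseline, nobody can check whether those remaining were alike on EPS at entry. This limits what can be checked; it does not demonstrate bias.

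**The case against.** The strongest reply is that randomisation does the work. Step 5 bears this out, and it stands. A reader might infer from the missing baseline that the arms cannot be compared on the ESRS-A at all; the documents do not support that.

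A reader might also point to chance imbalance. At 50 per arm, with 5%, 10% or 20% pre-existing symptoms, the between-arm difference at baseline has a standard deviation of √[2p(1 − p)/50], or 4.4, 6.0 or 8.0 percentage points. This is ordinary sampling variation, already part of the uncertainty of any between-arm difference, and the prevalences are assumed. It is not evidence of harm. Nor is a gain in precision from baseline adjustment: the plan has no ESRS-A model, test or confidence interval that would benefit.

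It is tempting to call the ESRS-A a named differentiating endpoint. The protocol lists it as one item among general safety assessments; linking it to the study's differentiating purpose is a fair inference, not the protocol's label. Nor is it the only safety scale without a baseline: SAP Table 1 has the Physician Withdrawal Checklist collected once only, after dosing.

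There is real mitigation. EPS reported as adverse events are classed as treatment-emergent by onset (SAP 6.1), and investigators are told to watch for tremor and ataxia (Protocol 9.7). Prior tardive dyskinesia and neuroleptic malignant syndrome are excluded, and recent antipsychotic use is barred. This narrows the gap to the rated scale but does not fill it. No pre-dose rating results, and SAP 6.1 plans grouped summaries for somnolence-related events and events of special interest, not for EPS.

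Finally, the latest SAP is dated 3 July 2019 and describes some data collection in the past tense, so a new Day 1 rating may reach few subjects or none. That stands and shapes the fix.

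**Conclusion.** The point holds as a cheap improvement to a descriptive secondary safety measure. No pre-dose ESRS-A exists, so each arm's frequencies are post-baseline prevalence, and neither change nor treatment-emergent worsening can be derived, although the protocol includes the scale to monitor drug-induced symptoms. With no placebo arm, no reference group shows the background level either.

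The comparison between arms remains unbiased by pre-existing symptoms in expectation, subject to the qualification about later visits. The primary endpoint and every formal test are untouched, and no figure in the documents changes.

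The size of the mixing is unknown. The 34% to 71% range rests on assumed pre-existing prevalences of 5% to 20%, full persistence, and 10% new onset among the rest. It illustrates what the tables cannot show and is not an estimate for this trial. That no baseline can be derived rests on the documents alone.

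**What to change.** For subjects not yet dosed:
- Add the ESRS-A to the Time and Events Schedule at Visit 2 (Day 1, before the first dose).
- Add a baseline row for the ESRS-A to SAP Table 1.
- Add to SAP 6.5.3 a shift from baseline to the worst double-blind score, by arm, for each of the 24 items and the 4 subscales.

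For subjects already dosed without a baseline:
- State in SAP 6.5.3 that the ESRS-A is interpreted only as a between-arm comparison of post-baseline prevalence. The section does not call its output drug-induced, so this is a limit on interpretation and not a relabelling.
- Pre-specify in SAP 6.1 a grouped EPS/akathisia summary of treatment-emergent adverse events by arm, with its preferred terms listed before unblinding.

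The cost is one more rating at an existing visit, of a scale that sites already give at five scheduled visits; no new staff or equipment is needed. The SAP changes cost one table and one event grouping. If all subjects have been dosed, only the second set applies, and the missing baseline cannot be recovered.

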**Abbreviations:**

AE=adverse event, ASEX=Arizona Sexual Experiences Scale, CGI-S=Clinical Global Impression – Severity, CSD-M=Consensus Sleep Diary-Morning Administration Version, C-SSRS =Columbia Suicide Severity Rating Scale, ECG=electrocardiogram, ESRS-A= Extrapyramidal Symptom Rating Scale-Abbreviated, FSH=follicle stimulating hormone, FT4= free thyroxine, HAM-A=Hamilton Anxiety Rating Scale, HbA1c=hemoglobin A1c, HRUQ=Healthcare Resource Use Questionnaire, HVLT-R=Hopkins Verbal Learning Test-Revised, ISI = Insomnia Severity Index, MADRS = Montgomery-Åsberg Depression Rating Scale, MGH-ATRQ=Massachusetts General Hospital-Antidepressant Treatment Response Questionnaire, PK=pharmacokinetic, PGx=pharmacogenomic, PGI-S= Patient Global Impression-Severity, PROMIS-SD =Patient Reported Outcomes Measurement Information System-Sleep Disturbance, PROMIS-SRI=Patient Reported Outcomes Measurement Information System-Sleep-Related Impairment, PWC=Physician Withdrawal Checklist, QLDS =Quality of Life in Depression Scale, SCID-CT = Structured Clinical Interview for DSM-5 Axis I Disorders– Clinical Trials Version, SDMT = Symbol Digit Modalities Test, SMDDS= Symptoms of Major Depressive Disorder Scale, SIGH-A=structured interview guide for the Hamilton Anxiety Scale, SIGMA=structured interview guide for the Montgomery-Asberg Depression Rating Scale, TMT- Part B =Trail Making Test Part B, TSH= thyroid-stimulating hormone.

- Unscheduled visits may be made at the discretion of the investigator. Adverse events, concomitant medications, and C-SSRS should be collected at all visits. Dose adjustment of study medication can only be made during an in-person study visit. If the dose is changed, then at a minimum the CGI-S, PGI-S, and SMDDS should be collected along with the ESRS-A.
- End-of-study/follow-up assessments will be conducted within 7 to 14 days after the last dose in the double-blind treatment phase. If a subject discontinues study treatment before the end of the double-blind phase, end-of-study/follow-up assessments should be obtained as soon as possible.
- A telephone interview will be conducted at the end of Week 1 to collect any adverse events and assess any other issues with tolerability to the study medication.
- Must be signed before first study-related activity.

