**Table 2: Dose Description**

Dose Level	Capsules
20-mg JNJ-42847922	20 mg and placebo
40-mg JNJ-42847922	20 mg and 20 mg
50-mg Quetiapine XR	50 mg and placebo
150-mg Quetiapine XR	150 mg and placebo
300-mg Quetiapine XR	150 mg and 150 mg

All subjects randomized to JNJ-42847922 will receive 20 mg as a starting dose. Subjects randomized to quetiapine XR will receive 50 mg once daily for 2 days, followed by an increase to 150 mg once daily on Day 3, as per prescribing guidelines in the product label. After the initial dosing period, dose adjustments may be made starting with the first scheduled clinic visit (Day 14). The first dose adjustment must be upwards. Subsequent adjustments may be made upwards or downwards within the study dose ranges (20 or 40 mg for subjects randomized to JNJ-42847922 or 150 or 300 mg for subjects randomized to quetiapine XR) if necessary, depending upon the investigator's assessment of the subject's clinical response and tolerability.

Adjustments of dose should only be made after a clinic visit (if needed may be an unscheduled visit) and assessment of efficacy and tolerability of the medication.

Subjects for whom tolerability at the lowest dose is either unacceptable or cannot be appropriately managed should be withdrawn from the study, and the AE recorded as a reason for discontinuation. For subjects on the highest doses, if there is a lack of response after a clinically appropriate treatment time, the investigator should consider discontinuing the subject due to lack of efficacy.

Subjects will administer the assigned study drug once daily at bedtime, approximately 3 hours after the last meal, from Day 1 to Day 167. Subjects are required to record the administration of study drug or any missed doses in subject diaries, which will be checked at each scheduled visit. The capsules must be swallowed whole and not chewed, divided, dissolved or crushed (see [Table 3](#)) for description of interventions.

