### **Extrapyramidal Symptom Rating Scale—Abbreviated (ESRS-A)**

Results from the ESRS-A will be tabulated by treatment.

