2.3. Visit Windows

As subjects do not always adhere to the protocol visit schedule, the following rules are applied to assign actual visits to analysis visits. Listed below are the visit windows and the target days for each visit. The reference day is Study Day 1 (which is the first day the study agent was taken in the double-blind phase). If a subject has 2 or more actual visits in one visit window, the visit closest to the target day will be used as the protocol visit for that visit window. The other additional visit(s) will not be used in the summaries or analyses but they can be used for determination of clinically important endpoints. If 2 actual visits are equidistant from the target day within a visit window, the later visit is used.

All assignments will be made in chronological order. Once a visit date is assigned to a visit window, it will no longer be used for a later time point except for the end point (DB). Listed below (Table 1) are the visit windows and the target days for each visit defined in the protocol.

Table 1 – Visit Windows

Parameter	Analysis Phase	Scheduled Visit Number	Time Interval (label on output)	Time Interval (Day)*	Target Time Point (Day/Time)
MADRS, Vital Signs, C-SSRS	Screening	1	Screening	<1	-28 to -1
	DB	2	Baseline	≤1	1
		4	Week 2	2 to 21	14
		5	Week 4	22 to 35	28
		6	Week 6	36 to 63	42
		7	Week 12	64 to 105	84
		8	Week 18	106 to 147	126
		9	Week 24	148 to end of DB	168
	DB last visit	End point (DB)	2 to end of DB		
Follow-up	10	Follow-up	End of DB + 1 to end of FU	182	
CGI-S, PGI-S	DB	2	Baseline	≤1	1
		4	Week 2	2 to 21	14
		5	Week 4	22 to 35	28
		6	Week 6	36 to 63	42
		7	Week 12	64 to 105	84
		8	Week 18	106 to 147	126
		9	Week 24	148 to end of DB	168
	DB last visit	End point (DB)	2 to end of DB		
	Follow-up	10	Follow-up	End of DB + 1 to end of FU	182
HAM-A	DB	2	Baseline	≤1	1
		6	Week 6	2 to 63	42
		7	Week 12	64 to 105	84
		8	Week 18	106 to 147	126
		9	Week 24	148 to end of DB	168
	DB last visit	End point (DB)	2 to end of DB		
Follow-up	10	Follow-up	End of DB + 1 to end of FU	182	
SDMT, TMT-Part B, HVLT-R	DB	2	Baseline	≤1	1
		6	Week 6	2 to 63	42
		7	Week 12	64 to 126	84
		9	Week 24	127 to end of DB	168
DB last visit	End point (DB)	2 to end of DB			
QLDS, SMDDS	DB	2	Baseline	≤1	1
		4	Week 2	2 to 21	14
		5	Week 4	22 to 35	28
		6	Week 6	36 to 63	42
		7	Week 12	64 to 105	84
		8	Week 18	106 to 147	126
		9	Week 24	148 to end of DB	168
	DB last visit	End point (DB)	2 to end of DB		
PROMIS-SD, PROMIS-SRI	DB	2	Baseline	≤1	1

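### The planned ESRS-A tables are per visit only, so scale-based incidence and worst severity of EPS or akathisia per arm cannot be read from them

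*SAP*

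**What the plan says.** EPS measured by the ESRS-A is a listed safety endpoint (Protocol 2.1). The reason is given under Safety Evaluations in Protocol 3.2: "The ESRS-A is being included since the comparator medication, quetiapine XR, is an antipsychotic with the potential to cause EPS and akathisia". Protocol 11.8 commits only to this: "Results from the ESRS-A will be tabulated by treatment". SAP 6.5.3 carries that out by time point: "a frequency distribution will be provided by treatment group at each time point".

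In SAP Table 1 the ESRS-A time points are Weeks 2, 4, 6, 12 and 24, plus End point (DB). The last of these is not a worst value: "End point (DB) is defined as the last available postbaseline result within the double-blind phase".

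Ratings are also taken outside that schedule. The notes to the Time and Events Schedule say: "If the dose is changed, then at a minimum the CGI-S, PGI-S, and SMDDS should be collected along with the ESRS-A". Protocol Section 6 allows a dose change at an unscheduled visit. SAP 2.3 then keeps one visit per window, the one closest to target, and says of the rest: "The other additional visit(s) will not be used in the summaries or analyses". The same sentence goes on to allow those visits to be used in determining clinically important endpoints, but SAP 6.5.3 defines no such endpoint for the ESRS-A.

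Other safety scales are handled differently from one another. SAP 6.5.1 (C-SSRS) plans the maximum postbaseline score and a listing. SAP 6.4 (ECG) plans maxima over scheduled and unscheduled visits. SAP 6.5.2 (ASEX) is per visit only.

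**The concern.** The study is meant to find features that separate JNJ-42847922 from quetiapine XR, and EPS and akathisia are plausible candidates. The natural safety questions are how many subjects in each arm ever showed signs on the scale, and how severe those signs became. A set of visit-by-visit frequency tables answers neither. It does not link a subject's ratings across visits, and the last-value summary misses signs that resolved earlier. Without a listing, the link cannot be rebuilt from the planned outputs.

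Ratings prompted by a dose change add to this. After Week 6 the scheduled ESRS-A visits are only Weeks 12 and 24, so a rating at an unscheduled visit, or at a Week 18 dose change, may be the only scale record of a passing episode. It will usually not reach the tables.

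**Working it through.** The documents give no figure for the ESRS-A analysis, so there is none to reproduce.

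**1. What per-visit counts leave open.** Inputs: 50 subjects per arm (SAP 1.4) and five scheduled ratings (SAP Table 1). The per-visit count *x* is assumed, and all 50 subjects are taken as rated at every visit. The number ever non-zero lies between *x* (the same subjects each time) and min(50, 5*x*) (different subjects each time).

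| Non-zero at each visit | Fewest ever affected | Most ever affected |
|---|---|---|
| 3 of 50 | 3 (6%) | 15 (30%) |
| 5 of 50 | 5 (10%) | 25 (50%) |

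Two arms with identical tables could in principle stand at 5/50 and 25/50.

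**2. When an extra rating reaches the per-visit tables.** Inputs: ESRS-A windows of Days 2–21, 22–35, 36–63, 64–126 and 127 to end, with targets 14, 28, 42, 84 and 168; the closest visit is kept and ties go to the later one. Dose changes start at Day 14, so unscheduled visits on Days 15–167 are considered (153 days, less any scheduled ESRS-A visit days among them).

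- All scheduled visits attended on target: the extra rating enters on 0 of 150 days.
- One scheduled visit missed, the others on target: 14 of 151 (Week 4), 28 of 151 (Week 6), 63 of 151 (Week 12), 41 of 150 (Week 24).
- Most favourable timing within the visit windows (Days 11, 25, 38, 77 and 175): 37 of 150.
- A Week 18 rating (Days 119–133) lies 35 to 42 days from the target of its window, against at most 7 for an in-window Week 12 or Week 24 visit.

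An extra rating that is the last double-blind result still enters End point (DB). Dose changes at Weeks 2, 4, 6 and 12 normally keep their rating, because an ESRS-A is scheduled there. The documents do not say how many dose changes will be unscheduled, so the number of ratings left out is unknown.

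**3. What a worst-score summary would and would not show.**

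*Recall.* Each rating covers 7 days: 5 × 7 = 35 of 168 days, about 21%.

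*All ratings.* With an assumed independent chance *q* of a non-zero score at each rating, P(ever non-zero) = 1 − (1 − *q*)^k. For *q* = 2%, 5% and 10%, five ratings give 10%, 23% and 41%; seven ratings give 13%, 30% and 52%. Two extra ratings therefore add about 4 to 11 points with no true difference.

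*Scheduled ratings plus a withdrawal rating.* Planning assumptions (SAP 1.4): 50% discontinue quetiapine XR and the hazard ratio is 0.415, which gives 1 − 0.5^0.415 = 25% for JNJ-42847922. With exponential discontinuation, scheduled ratings per subject are the sum of S(t) at Days 14, 28, 42, 84 and 168: 3.88 for quetiapine XR and 4.48 for JNJ-42847922. Adding one rating per early withdrawal gives 3.88 + 0.50 = 4.38 and 4.48 + 0.25 = 4.73. Averaging 1 − (1 − *q*)^k over the resulting number of ratings:

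| q | Quetiapine XR | JNJ-42847922 | Gap (points, before rounding) |
|---|---|---|---|
| 2% | 8.4% | 9.1% | 0.6 |
| 5% | 20.0% | 21.5% | 1.5 |
| 10% | 36.5% | 39.0% | 2.5 |

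**The case against.** The strongest reply is that per-subject EPS incidence is already planned through adverse events. Protocol 9.7 requires clinically relevant changes to be recorded as adverse events and asks investigators to watch for CNS events, tremor among them. SAP 6.1 counts subjects per arm by preferred term, by severity, by discontinuation and by dose modification. This stands in large part. A reader might infer that EPS incidence will go unreported; the documents do not support that. What is missing is incidence on the scale. SAP 6.1 groups somnolence terms but defines no EPS or akathisia group.

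A second reply is that nothing promised is withheld. That is right. A reader might infer a conflict between protocol and SAP, but the protocol promises only tabulation by treatment, and SAP 6.5.3 delivers it. Nor is a maximum the SAP's uniform standard, as ASEX shows. The absence of a Week 18 ESRS-A window follows the visit schedule and is not an error.

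A third tempting reading is that dose-change ratings are discarded outright. SAP 2.3 does not go that far: it leaves room to use extra visits for clinically important endpoints. Because none is defined for the ESRS-A, that allowance does not fill the gap.

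Finally, a maximum can mislead. It depends on how many ratings a subject has, it misses episodes outside the recall period, and without a baseline rating it cannot separate pre-existing from new signs. All of this stands. It argues for labelling and disclosure rather than for leaving the summary out.

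**Conclusion.** The concern holds as a minor, descriptive gap. It touches no test, primary endpoint or decision rule. From the outputs planned in SAP 6.5.3, scale-based incidence and worst severity per arm cannot be determined.

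The 5-to-25 range is a logical bound. It assumes complete ratings and opposite extremes of recurrence, and says nothing about what is likely.

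The 0.6 to 2.5 point gap rests on exponential discontinuation at the planning rates and an equal, independent risk at every rating. A reader might infer that a scheduled-ratings maximum must understate quetiapine XR. The documents do not support a direction: withdrawal ratings may be taken when symptoms are present, which would push the other way.

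**What to change.** In SAP 6.5.3, keep the per-visit tables and add, by treatment group:

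- The distribution of each subject's maximum double-blind score for each item and each of the 4 CGI-MS subscales, in two versions: (a) over scheduled ratings, including an early-withdrawal rating that falls in the double-blind phase, for the between-arm comparison; (b) over all ratings, including unscheduled ones.
- The number of ratings per subject.
- A listing of subjects with any non-zero CGI-MS score.

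Label the summary *worst on-treatment*, and state the limits beside it: 7-day recall, no baseline rating, possible inflation of version (b) in the arm with more dose changes, and unequal numbers of ratings in version (a).

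The cost is a few sentences in the SAP, one table in two versions, one count and one listing, with no new data collection. The label and the rating counts disclose the limits but do not remove them.
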